6.3 Availability

Metformin HCl ER 500 mg tablet (NDC 62037-0571-01; Actavis, Parsippany, NJ, formerly Watson Laboratories, Corona, CA) will be supplied to investigators by the NCI, DCP.

6.4 Agent Distribution

Agents will only be released by NCI, DCP after documentation of IRB approval of the DCP-approved protocol and consent is provided to DCP and the collection of all Essential Documents is complete (see DCP website for description of Essential Documents).

NCI, DCP-supplied agents may be requested by the Investigator (or their authorized designees) at each Organization. DCP guidelines require that the agent be shipped directly to the institution or site where the agent will be prepared and administered. DCP does not permit the transfer of agents between institutions (unless prior approval from DCP is obtained). DCP does not automatically ship agents; the site must make a request. Agents are requested by completing the DCP Clinical Drug Request form (NIH-986) (to include complete shipping contact information) and faxing or mailing the form to the DCP agent repository contractor:

[name]
MRIGlobal
DCP Repository
[name]
[name]
[contact]
[contact]
Emergency [contact]

6.5 Agent Accountability

The Investigator, or a responsible party designated by the Investigator, must maintain a careful record of the inventory and disposition of all agents received from DCP using the NCI Drug Accountability Record Form (DARF). The Investigator is required to maintain adequate records of receipt, dispensing and final disposition of study agent. This responsibility has been delegated to the research/investigational pharmacy staff at each site. Include on receipt record from whom the agent was received and to whom study agent was shipped, date, quantity and batch or lot number. On dispensing record, note quantities and dates study agent was dispensed to and returned by each participant.

6.6 Packaging and Labeling

DCP will package, label and distribute agent for all DCP-supplied agents.

6.7 Storage

Metformin HCl ER tablets should be stored at 20–25°C (68–77 °F) in a secure, locked area of the research facility, with excursions permitted to 15–30 °C (59–86°F).

6.8 Registration/Randomization

Participants will be considered registered on the date they sign the approved informed consent document with a member of the study staff. The study coordinator will contact the UAZ Consortium Office for a participant identification number (PID) when the subject has been consented. This study does not involve randomization.

6.9 Blinding and Unblinding Methods

Not applicable.

6.10 Agent Destruction/Disposal

DCP-supplied agents: at the completion of investigation, all unused study agent will be returned to NCI, DCP Repository according to the DCP “Guidelines for AGENT RETURNS” and using the DCP form “Return Drug List”.

7. CLINICAL EVALUATIONS AND PROCEDURES

7.1 Schedule of Events

Evaluation/ Procedure ¹	Baseline	Agent Start Day 1 of Week 1	Weeks 1-5	Week 6 (± 1 week)	Weeks 7-11	Week 12-14 or Early Termination	Follow-Up (2-4 weeks post- intervention)
Informed Consent	X						
Assess Eligibility	X						
Medical History	X			X		X	
Vital Signs ² / Height ³ and Weight	X			X		X	
Physical Exam ⁸	X			X		X	
Performance status	X						
Concomitant medications	X		X	X	X	X	X
Assessment of tobacco and alcohol use	X					X	
Fasting blood for CBC/diff, CMP ⁷ , C- peptide, HbA1c	X					X	
Urine pregnancy test if applicable	X	X ⁴		X		X	
Examination of oral cavity	X			X		X	
Lesion measurement	X			X		X	
Photography	X			X		X	
Biopsies ⁵	X					X	
Saliva collection for research biomarkers ¹⁰	X					X	
Fasting blood collection for research biomarkers	X					X	
Dispense Study Agent ⁴		X		X			
Collect Study Agent				X		X	
Review Agent Diary/Record				X		X	
Adverse Events			X	X	X	X	X
Telephone/Email Contact			X ⁶		X ⁹		X

¹ Initiation of study agent should occur within 9 weeks of baseline biopsy. On-study evaluations should be conducted with the following timeframes: week 6 interim visit can be scheduled +/- 1 week; total agent intervention duration is 12 – 14 weeks; post-intervention visit can be scheduled between weeks 12-14; the agent should be taken until the evening before the post-intervention visit.

² Vital signs include temperature, blood pressure, and pulse.

³ Only at baseline.

⁴ Eligible participants may have agent shipped to them. Urine pregnancy test for women of childbearing potential does not need to be repeated at agent start if the baseline test was done within 4 weeks prior to agent start.

⁵ At baseline, a biopsy will be performed on the lesion that meets the size criteria or on the largest lesion, if multiple lesions that meet the size criteria. If smaller lesions meet the size criteria and are of clinical concern to treating physician, they may be biopsied. The lesion with the worst histology following the central pathology review will be the target lesion and re-biopsied at post-intervention. If the target lesion is not visible post-intervention, a biopsy will be obtained at the site of the previous lesion biopsy. Biopsy of visually normal cheek mucosa will be obtained at baseline and post-intervention.

⁶ Telephone (or email) contact within 3 days of starting the agent and before and after each dose escalation. Participants are eligible for dose escalation only in the absence of grade 2 or higher toxicities.

⁷ CMP includes serum glucose, urea nitrogen, creatinine, sodium, potassium, chloride, bicarbonate, total protein, albumin, calcium, alkaline phosphatase, ALT, AST, total bilirubin. Calculations included with the CMP are: BUN/creatinine ratio, anion, gap, globulin, alb/glob ratio, eGFR.

⁸ Physical exam includes assessment of chest, heart, abdomen, and lower extremities for pedal edema.

⁹ Telephone (or email) contact at Week 9 (± 3 days).

¹⁰ Saliva should be collected between 8 am and 12 noon, if feasible.

7.2 Baseline Testing/Prestudy Evaluation

Participants will undergo a Baseline Testing/Pre-Study Evaluation in which the informed consent form and medical records release and tissue release form will be signed. Participants will be assessed for study eligibility. This clinic visit should be scheduled between 8 am and 12 noon, when feasible.

Participants will undergo a brief physical exam including assessment of chest, heart, abdomen, and lower extremities for pedal edema. Weight, height, vital signs (temperature, blood pressure, pulse) and performance status will be collected.

Participants will also be evaluated for concomitant medications, medical history, baseline symptoms and signs, and assessment of tobacco and alcohol use. The tobacco and alcohol history will be recorded directly onto the CRF which will be considered the source document for these data.

Participants will undergo an oral exam for lesion measurement and photography. Bi-dimensional measurements for all lesions will be recorded. All lesions that meet the size criteria ($\geq 8 \times 3 \text{mm}$) will be considered target lesions for clinical response assessment. Lesions that do not meet the size criteria ($< 8 \times 3 \text{mm}$) will be measured but recorded as non-measurable. Color photographs of all lesions will be taken. A biopsy will be performed on the lesion that meets the size criteria or on the largest lesion, if multiple lesions meet the size criteria. If smaller lesions meet the size criteria and are of clinical concern to treating physician, they may be biopsied. All biopsies will be sent for local pathology evaluation, followed by central pathology review. The lesion with the worst histology following the central pathology review will be selected as the target lesion for histologic response assessment and for tissue biomarker evaluation.

If participant underwent a pre-enrollment biopsy within 6 weeks prior to the Baseline visit and the pre-enrollment biopsy has been histologically confirmed with adequate archival tissue for biomarker analysis, a biopsy of the lesion will not be obtained at the Baseline clinic visit. Rather, archival tissue will be collected. In these participants, the same size criteria for eligibility apply.

The final histologic eligibility will be determined by a centralized pathology review (see section 10.2).

Biopsy of visually normal cheek mucosa will be performed on all participants to evaluate tissue markers, including those who had a prior lesion biopsy that is qualifying.

Saliva will be collected for metformin levels and cytokine biomarkers. Saliva should be collected between 8 am and 12 noon, if feasible.

Fasting blood will be collected for complete blood count with differential (CBC-diff), comprehensive metabolic panel (CMP), C-peptide, and HbA1c. Fasting blood will also be collected for serum metformin levels, serum cytokine biomarkers, and genomic analysis of blood DNA.

Urine pregnancy test will be performed for potentially fertile women.

Participants may return within 7 days of the Baseline Testing/Pre-Study Visit for procedures not performed during the Baseline Testing/Pre-Study Visit. Participants will be provided with an AE Diary and instructions on how to complete the AE Diary.

7.3 Evaluation During Study Intervention

After eligibility is confirmed, participants will be provided with an initial supply of metformin ER 500 mg tablets and an Intake Calendar (agent/medication log). The agent supply and Intake Calendar may be provided to the participants during a clinic visit or may be mailed to the participants, although potentially

fertile women will need to have a negative urine pregnancy test within 4 weeks before provision of agent supply. Initiation of study agent should occur within 9 weeks of baseline biopsy.

Participants will be instructed on how to complete the Intake Calendar. The Calendar will be marked with agent start date and dosage increase dates. Participants will be instructed to take Metformin ER 500 mg per day for one week, followed by dose escalation to 1,000 mg per day for one week, followed by dose escalation to 2,000 mg/day for the remainder of the 3 month period. Suitability for dose escalation will be assessed via telephone (or email) contact prior to starting the intervention and each escalation as participants are eligible for dose escalation only in the absence of grade 2 or higher toxicities. Additional telephone (or email) contact will also be made following dose escalation. There will be an additional interim telephone (or email) contact at week 9 (\pm 3 days) to assess adverse events and encourage compliance.

An interim clinic visit will occur after 6 (\pm 1) weeks of treatment. During this visit, participants will undergo a brief physical assessment of the chest, heart, abdomen, and lower extremities for pedal edema, be assessed for changes in medical history, and be evaluated for weight and vital signs. They will return unused pills. Unused pills will be counted and may be re-issued along with a new supply of study pills. AEs, concomitant medications, and compliance will be reviewed. A urine pregnancy test will be repeated, if applicable.

Participants will undergo an oral exam for lesion measurement and photography. Bi-dimensional measurements for all lesions will be recorded. Lesions that do not meet the size criteria ($<8 \times 3$ mm) will be measured but recorded as non-measurable. Color photographs of all lesions will be taken.

7.4 Evaluation at Completion of Study Intervention

Participants will return after 12-14 weeks of agent intervention for post-intervention evaluation. This visit should be scheduled between 8 am and 12 noon because of the saliva collection. During this visit, participants will return unused pills and be evaluated for weight, vital signs, AEs, concomitant medications, and tobacco and alcohol assessment. They will undergo a brief physical assessment of the chest, heart, abdomen, and lower extremities for pedal edema and be assessed for changes in medical history. The tobacco and alcohol history will be recorded directly onto the CRF which will be considered the source document for these data.

Participants will undergo an oral exam for lesion measurement and photography. Bi-dimensional measurements for all lesions will be recorded. Lesions that do not meet the size criteria ($<8 \times 3$ mm) will be measured but recorded as non-measurable. Color photographs of all lesions will be taken.

A biopsy will be performed on the selected target lesion for histopathology and tissue markers. If the target lesion is not visible post-intervention, a biopsy will be obtained at the site of the previous lesion biopsy. A biopsy of visually normal cheek mucosa will be performed for tissue markers.

Saliva will be collected for metformin levels and cytokine biomarkers.

Fasting blood will be collected for complete blood count with differential (CBC-diff), comprehensive metabolic panel (CMP), C-peptide, and HbA1c. Fasting blood will also be collected for serum trough metformin levels and serum cytokine biomarkers. Urine pregnancy test will be repeated, if indicated.

7.5 Post-intervention Follow-up Period

Participants will be contacted by telephone (or email) 2-4 weeks later for a final AE assessment of drug, and to be provided with final biopsy report. Participants will be reminded to return the AE Diary to the study office in a pre-stamped envelope.

7.6 Methods for Clinical Procedures

7.6.1 Measurement of lesions

All lesions will be measured in a bi-directional plane. The lesion length is the longest side and the width is perpendicular to the longest length. Lesions that do not meet the size criteria (<8x3mm) will be measured but recorded as non-measurable. The bi-directional measurements will be recorded on standard head and neck cancer staging maps. For example:

Lesion #1 8 mm length x 3 mm width = 24 mm² (product)

Lesion #2 9 mm length x 3 mm width = 27 mm² (product)

7.6.2 Lesion photographs

Color photographs of all lesions will be obtained prior to biopsy and digitally stored for the documentation of clinical response, however, the investigators' lesion measurements will be the official measurements for baseline and post-treatment assessments. For monitoring purposes, the participant's initials and PID will be on each photograph.

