4. PARTICIPANT SELECTION

4.1 Inclusion Criteria

4.1.1 Participants with oral leukoplakia or erythroplakia with mild, moderate, or severe histologic dysplasia, or hyperplasia not associated with mechanical factors such as ill-fitted dentures.

4.1.2 Measurable disease – minimum lesion size of 8x3 mm before initial biopsy.

4.1.3 Age \geq 18 years.

4.1.4 Karnofsky performance status \geq 70%.

4.1.5 Participants must have normal organ and marrow function as defined below:

Leukocytes	\geq 3,000/microliter
Absolute neutrophil count	\geq 1,000/microliter
Platelets	\geq 100,000/microliter
Total bilirubin	\leq 1.5 \times institutional ULN
AST (SGOT)/ALT (SGPT)	\leq 1.5 \times institutional ULN

eGFR $>$ 40 mL/min using the Cockcroft-Gault equation
(<http://www.mdcalc.com/creatinine-clearance-cockcroft-gault-...equation/>).

4.1.6 Life expectancy $>$ 3 months.

4.1.7 Willing to use adequate contraception (barrier method, abstinence, subject has had a vasectomy or partner is using effective birth control or is postmenopausal) for the duration of study participation because the effects of metformin on the developing human fetus are unknown even though it is not teratogenic in rats and rabbits at 2-6 times the maximum recommended human daily dose.

4.1.8 Ability to take oral medication.

4.1.9 Ability to understand and the willingness to sign a written informed consent document.

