13.2 Randomization/Stratification

This is a single-arm, open-label trial so no randomization, stratification or blocking will be performed. Also, no formal interim analysis is planned.

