13.4 Primary Objective, Endpoint(s), Analysis Plan

The primary objective of this study is to determine whether 12-14 weeks of treatment with therapeutic doses of metformin would improve the clinical response of oral premalignant lesions. Each participant's clinical response will be categorized into Complete Response (CR), Partial Response (PR), No Change (NC) or Progressive Disease (PD), evaluated by the criteria described in § 8.1. A participant with CR or PR is considered as a respondent. The preclinical data demonstrate that metformin defers carcinogen-induced HNSCC development and progression (see §2.3). Based on the positive preclinical data, the main interest of this study is in measuring and evaluating the improvement not in evaluating the unlikely negative effect. Therefore, a one-sided one-sample binomial exact test at a significance level of 5% will be performed to see if the clinical response rate is greater than 30% (poor treatment). A sample size of 20 achieves 87% power to detect a response rate 0.30 higher than a poor treatment response.

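### Clinical response rests only on open-label investigator readings, with no same-examiner rule, no withholding of earlier diameters and no scale in the photographs, so a small lean can turn a partly shrunken No Change lesion into a Partial Response.

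*Combined protocol and SAP*

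**What the plan says.** Section 13.2 describes the design: "This is a single-arm, open-label trial so no randomization, stratification or blocking will be performed". Section 6.9, on blinding, is marked not applicable.

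Section 8.1 defines Partial Response (PR) as a fall of at least 50% in the summed products of the two diameters, over lesions measurable at baseline. No Change is whatever is not CR, PR or PD. Section 13.4 then dichotomises: "A participant with CR or PR is considered as a respondent". The responder proportion is tested one-sided at 5% against 30% by an exact binomial test, with 20 participants and a stated power of 87%.

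On measurement, Section 7.6.1 says: "The bi-directional measurements will be recorded on standard head and neck cancer staging maps". Section 7.6.2 has photographs "digitally stored for the documentation of clinical response", but states that the investigators' "lesion measurements will be the official measurements for baseline and post-treatment assessments". The smallest measurable lesion is set in Section 4.1 ("minimum lesion size of 8x3 mm before initial biopsy").

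Sections 3, 7.2 to 7.4, 7.6.1, 7.6.2 and 8.1 do not mention the same examiner across visits, withholding of earlier diameters, duplicate or independent measurement, or a scale in the photographs. Central review (Section 10.2) covers histology only, which is a secondary endpoint.

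**The concern.** The examiner at week 12-14 knows that the participant has taken metformin. Nothing in the plan stops that examiner from seeing the baseline diameters before measuring. The reading feeds a cut-off on a product of two diameters, so an error in each diameter compounds.

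In a randomised trial a lean shared by both arms would largely cancel. Here the comparator is the constant 30%, so any net movement of participants from No Change to PR counts as treatment effect. The photographs could serve as a check, but the plan asks for no millimetre scale in them, and one cannot be added afterwards. A positive result would be open to an objection that is cheap to limit in advance.

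**Working it through.** **Reproducing the plan's figure.** Inputs from Sections 13.1 and 13.4: n = 20, p0 = 0.30, p1 = 0.60, one-sided 5%, exact binomial.

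- P(X ≥ 9 | 0.30) = 0.113 and P(X ≥ 10 | 0.30) = 0.048, so the rule is to reject at 10 or more responders.
- Power = P(X ≥ 10 | 0.60) = 0.872, which agrees with the stated 87%.

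**Effect of a 1 mm lean.** The documents give no measurement-error figure, so the 1 mm is my assumption. Let L x W be the baseline diameters and l x w the true post-treatment diameters.

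- True fall = 1 − lw/(LW).
- Read fall, with both post-treatment diameters 1 mm short = 1 − (l − 1)(w − 1)/(LW).

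*Unchanged lesion (l = L, w = W).* The read fall is 1 − (1 − 1/L)(1 − 1/W), which decreases as L or W grows. Its maximum is therefore at the 8x3 minimum: 1 − (7 × 2)/24 = 10/24 = 41.7%. For 10x5 it is 1 − 36/50 = 28.0%, and for 20x10 it is 1 − 171/200 = 14.5%. With several measurable lesions, the fall in the sum is a weighted average of these and cannot exceed 41.7%. The 50% line is not reached.

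*Partly shrunken lesion, truly No Change:*

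| Baseline (mm) | True post | True fall | Read as | Read fall |
|---|---|---|---|---|
| 8x3 | 7x3 | 12.5% | 6x2 | 1 − 12/24 = 50% |
| 10x5 | 9x4 | 28% | 8x3 | 1 − 24/50 = 52% |
| 20x10 | 15x8 | 40% | 14x7 | 1 − 98/200 = 51% |

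Each crosses into PR. If both diameters shrink in proportion, the true fall needed before the lean reaches 50% is about 11% at 8x3, 26% at 10x5, 31% at 12x6 and 39% at 20x10. The exposed band narrows as lesions get larger.

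**Effect on the test.** Suppose a share f of true non-responders is scored PR and a share g of true responders is missed. The apparent rate under the null is 0.30(1 − g) + 0.70f, and the error is P(X ≥ 10) at that rate. Both shares are illustrative.

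| f | g | Apparent rate | One-sided error |
|---|---|---|---|
| 0 | 0 | 0.300 | 4.8% |
| 5% | 0 | 0.335 | 9.5% |
| 10% | 0 | 0.370 | 16.5% |
| 5% | 5% | 0.320 | 7.2% |
| 10% | 10% | 0.340 | 10.3% |

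The rows with g = 0 describe a one-directional lean. The rows with f = g describe equal misclassification both ways. That also raises the error, because under the null there are more non-responders than responders to misclassify.

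**The case against.** A reader might infer that a 1 mm lean in each diameter by itself produces responders. It does not: with a post-treatment lean only, an unchanged eligible lesion never gets past 41.7%, and a 20x10 lesion must first truly lose about 39%.

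A reader might also infer that the examiner has the baseline diameters to hand. The documents do not say so. They say that diameters go on staging maps, and they do not prevent the maps from being consulted. Nor do they support the claim that a change of examiner adds noise as large as the PR and PD thresholds, since they give no reproducibility figure. Such noise also runs both ways: over-reading can block PR, or trigger PD through the 25% rule in Section 8.1.

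The 5% and 10% shares are not derived from the 1 mm error. That would need the distributions of lesion size and shrinkage, which the documents do not give.

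Finally, this is an exploratory phase IIa trial. Section 2.2 already defers any change of practice to a phase III study, and histologic response has independent review.

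All of this stands, and it limits the size of the point. It does not fill the gap: the primary endpoint alone carries the formal test, and its measurement has no safeguard against drift or expectation.

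**Conclusion.** The concern holds as a gap in measurement procedure. An unmasked two-diameter reading decides the primary endpoint against a fixed comparator. The plan does not require the same examiner, does not withhold earlier diameters, and leaves the photographs without a scale by which to check a reading.

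The effect is confined to lesions that have already shrunk somewhat. The true fall needed is small near the 8x3 minimum and approaches 40% at 20x10. How far the type I error would move is unknown; the range of 7.2% to 16.5% against 4.8% rests on assumed misclassification shares. The design and sample size stand. This is an inexpensive improvement that the sponsor should make, not a flaw that invalidates the trial.

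**What to change.** In Section 7.6.1, require that:

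- the same examiner measures a given participant at Baseline, week 6 and week 12-14 where possible, with a named back-up;
- at follow-up the examiner works from a location-only copy of the map, and records and signs the diameters before earlier diameters are shown.

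In Section 7.6.2, require a millimetre scale in each photograph already being taken, so that the official measurements can be checked.

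The cost is procedure wording, a second copy of the map without diameters, and a ruler in the frame. No extra visit, reader or procedure is needed. The downside is scheduling around one examiner per participant. These steps reduce expectation bias without removing it: the examiner still knows that metformin was given and may remember the baseline reading.
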